11.1.2 Prohibited Concomitant Medications

Drug Class/Medications	Comments
Amantadine	
Anorexiants (e.g., phentermine, phendimetrazine)	
Antibiotics (i.e., cefaclor, ceftizoxime, cephaloridine, and penicillin G). Antivirals (i.e., acyclovir, valacyclovir, ganciclovir, oseltamivir, and carboxylate)	Note: efficacy of these antibiotics will be minimally affected by SM, we recommend using a different class.
Anticholinesterase inhibitors	
Antipsychotics and long-acting injectable	
Anti-Parkinson medications (e.g., apomorphine, L-dopa, carbidopa-levodopa, COMT inhibitors, and MAO-B inhibitors)	
Baclofen	
Barbiturates	
Chloral hydrate, valerian	
Dextromethorphan	
Esketamine and off-label ketamine	Allowed in responders who have taken >6 months prior to screening and discontinued. Use of esketamine and off-label ketamine for treatment of depression <6 months prior to screening is not allowed. Other uses of ketamine should be discussed with the Medical Monitor for approval.
Eszopiclone	
Famotidine	Note: efficacy of famotidine can be minimally affected by SM, we recommend a different class of antiacid.
Furosemide	Note: efficacy of furosemide can be minimally affected by SM, we recommend a different diuretic.

Drug Class/Medications	Comments
Ketanserin	
Insulin	
Lithium, lamotrigine	
Memantine	
Methotrexate	Note: efficacy of methotrexate can be minimally affected by SM, when possible, we recommend using a different class of medication.
Viloxazine	
Opioids, tramadol	
Induced-QTc prolongation medications such as (not limited to): quinidine, disopyramide, chlorpromazine, haloperidol, risperidone, thioridazine, azithromycin, erythromycin, fluoroquinolones, levofloxacin, moxifloxacin, ketoconazole, terfenadine, and astemizole	
Reserpine	
Scopolamine	
St. John's Wort	
Tricyclic antidepressants, atypical antidepressants	Atypical antidepressants, e.g., mirtazapine, maprotiline, nefazodone, etc. Any off-label antidepressant medication use needs to be discussed and confirmed by the Medical Monitor prior to enrollment.
Thyroxine/T3, thyroid hormone prescribed for depression	
Trazodone (>150 mg/day)	Trazodone treatment before screening should be discontinued for a minimum of 5 half-lives before baseline.
Warfarin, anticoagulants medications, coumarins and indandionones, factor Xa inhibitors, heparins, antiplatelets, and direct thrombin inhibitors	

CGRP = calcitonin gene-related peptide; COMT = catechol-O-methyltransferase; IM = intramuscular; MAO-B = monoamine oxidase B; QTc = corrected QT interval; SM = study medication; T3 = triiodothyronine

11.2 Approved Antidepressant Treatment

This list includes all FDA approved antidepressants treatments allowed in the study.

Note: Subjects should be on 1 of the medications listed at a stable, therapeutic dose for at least 6 weeks before screening. If a subject is taking a second antidepressant or augmentation therapy at screening, the investigator should decide if it is medically appropriate to discontinue the second drug before randomization. In that case, the second drug should be discontinued at least 5 half-lives prior to baseline. If not, the subject should be excluded from the study.

Selective Serotonin Reuptake Inhibitors

Drug Name	Commercial Name	Minimally Adequate Dose	Minimal Dose at Optimal Level
Paroxetine	PAXIL, PAXIL CR, PEXEVA	20/25/25 mg/day	60/62.5/75 mg/day
Fluoxetine	PROZAC, SARAFEM, SYMBYAX	20 mg/day	60 mg/day
Sertraline	ZOLOFT	50 mg/day	150 mg/day
Citalopram	CELEXA	20 mg/day	60 mg/day
Escitalopram	LEXAPRO	10 mg/day	30 mg/day
Vortioxetine	BRINTELLIX/ TRINTELLIX	10 mg/day	20 mg/day
Vilazodone	VIIBRYD	40 mg/day	80 mg/day

Serotonin-Norepinephrine Reuptake Inhibitors

Drug Name	Commercial Name	Minimally Adequate Dose	Minimal Dose at Optimal Level
Venlafaxine / Venlafaxine XR	EFFEXOR, EFFEXOR XR	150/75 mg/day	250/225 mg/day
Duloxetine	CYMBALTA	60 mg/day	120 mg/day
Desvenlafaxine	PRISTIQ, KHEDEZIA	50 mg/day	100 mg/day
Levomilnacipran	FETZIMA	40 mg/day	120 mg/day

Other Antidepressants

Drug Name	Commercial Name	Minimally Adequate Dose	Minimal Dose at Optimal Level
Bupropion	WELLBUTRIN	300 mg/day	450 mg/day
Dextromethorphan/ Bupropion	AUVELITY	45/105 mg/day	90/110 mg/day

12 SUMMARY OF AMENDMENT CHANGES

Document History	
Document	Date
Version 3.0	14FEB2024
Version 2.0	01DEC2023
Version 1.0	09OCT2023

Amendment 3.0 (14 February 2024)

Supersedes previous version; date	Version 2.0; 01DEC2023
Current version; date	Version 3.0; 14FEB2024

Substantial changes to the protocol and their location within the protocol are summarized below. In addition, corrections of typographical errors that have been made throughout the protocol are not explained here.

Primary Reason for the Substantial Modification of the Protocol:

Revised select Inclusion Criteria to align with current clinical and regulatory definitions or guidance.

Summary of Changes

Section # Section Title	Description of Changes in Protocol Version Amendment Version 3.0; 14 February 2024	Brief Rationale for Change
Inclusion Criterion 8, Synopsis and Section 4.2.2 ; Global	Revised inclusion criterion #8 to include subjects that have received a stable dose of study-approved antidepressant for at least 6 weeks instead of 4.	To align with current clinical and regulatory definitions for adequate duration of treatment.
Exclusion Criterion 12, Synopsis and Section 4.2.2	Revised exclusion criterion #12 to update accepted timeframes for type 5 suicidal ideations based on C-SSRS and history of suicide attempt.	To better align with understanding of targeted study population
Inclusion Criterion 10 and 11, Synopsis and Section 4.2.2	Revised inclusion criterion #10 to remove sexual abstinence as an acceptable form of contraception in both sexes.	To align with current regulatory guidance for contraception in clinical studies.
Sections 4.1, 4.3, 6.3	Revised definition of study completers to include follow-up phone call on Day 12 (± 2).	Administrative clarification.
Section 7.4.1; Table 3: Clinical Laboratory Tests	Revised “Other” clinical laboratory tests to specify that “free” triiodothyronine (T3) and “free” thyroxine (T4) testing will be conducted.	Administrative clarification: T3 and T4 testing will not include bound T3 and T4 testing.
Section 11.1	Revised permitted and prohibited concomitant medication lists; removal of antiseizure medications as permitted medication.	Exclusion criterion #15 excludes subjects with history of seizure disorder.

11.1.	Schedule of Events and Assessments	28
11.2.	Clinical Laboratory Normalization.....	32

11.3.	Criteria for Clinically Notable Laboratory Values	33
11.4.	Normal Range for Vital Sign.....	34
11.5.	Criteria for Clinically Notable Vital Sign Values.....	34
11.6.	Normal Range for ECG	35

LIST OF TABLES

Table 1:	Study Objectives and Endpoints.....	9
Table 2:	Definitions and Derivations	12
Table 3:	Missing Date Imputation for Adverse Event or Concomitant Medication.....	13
Table 5:	Criteria for Clinically Notable Laboratory Values	33
Table 6:	Vital Sign Normal Ranges	34
Table 7:	Clinically Notable Vital Sign Values	34
Table 8:	ECG Normal Ranges	35

VERSION HISTORY

Version	Section	Description of Change	Rationale
1.0	NA	Original Version	NA

LIST OF ABBREVIATIONS

Abbreviation	Definition
AE	Adverse Event
ADT	Antidepressant Therapy
ATC	Anatomical Therapeutic Chemical
BDNF	Brain-Derived Neurotrophic Factor
BLQ	Below Limit of Quantification
BMI	Body Mass Index
BPRS	The Brief Psychiatric Rating Scale
CADSS	Clinician Administered Dissociative State Scale
CGI-S	Clinical Global Impression – Severity of Illness
C _{max}	Maximum Observed Concentration
C-SSRS	Columbia Suicide Severity Rating Scale
C _{trough}	Trough plasma concentration (Concentration at the end of dosing interval)
CFB	Change from Baseline
CI	Confidence Interval
CNV	Clinically Notable Values
eCRF	Electronic Case Report Form
CV%	Coefficient of variation expressed as a percentage
ECG	Electrocardiogram
EOS	End of Study
FAS	Full Analysis Set
FDA	Food and Drug Administration
HAM-D6	Hamilton Depression Rating Scale-6 Items
IPD	Important Protocol Deviation
LLOQ	Lower Limit of Quantification
MADRS	Montgomery–Åsberg Depression Rating Scale
MedDRA	Medical Dictionary for Regulatory Activities
MDD	Major Depressive Disorder
PD	Pharmacodynamics
PK	Pharmacokinetics
PT	Preferred term

Q1	First Quartile
Q3	Third Quartile
QTc	QT Interval Corrected for Heart Rate
QTcF	QT Interval Corrected for Heart Rate using Fridericia's Method
SAE	Serious Adverse Event
SAP	Statistical Analysis Plan
SD	Standard Deviation
SI	International System of Units
SM	Study Medication
SOC	System Organ Class
TEAE	Treatment-emergent Adverse Event
T _{max}	Time to Reach Maximum Observed Concentration (C _{max})
WHO-DD	World Health Organization Drug Dictionary

1. STUDY OBJECTIVES AND ENDPOINTS

The study objectives and other efficacy endpoints are described in Table 1.

Table 1: Study Objectives and Endpoints

Objectives	Endpoints

Primary Objective: To evaluate the efficacy of SPN-820 administered once every 3 days for a 7-day treatment period in adults with major depressive disorder (MDD).
	
Primary Efficacy Endpoint:
 
Change from baseline (CFB) to each time point in the Hamilton Depression Rating Scale-6 Items (HAM-D₆) total score. 
Secondary Efficacy Endpoints:
 
CFB to each time point in the Montgomery–Åsberg Depression Rating Scale (MADRS) total score.CFB to each time point in the Clinical Global Impression – Severity of Illness (CGI-S) total score.Proportion of subjects achieving a $\geq 50\%$ reduction from baseline in the MADRS total score.Proportion of subjects in remission (MADRS total score ≤ 10) at each time point.Percentage of subjects with a CGI-S score of 1 or 2 at each time point.

Secondary Objectives:
 
To evaluate the safety and tolerability of SPN-820 administered once every 3 days for a 7-day treatment period in adults with MDD.To characterize the pharmacokinetics (PK) of SPN-820 and its metabolite M8 in plasma after multiple administrations of SPN-820.	
Safety Endpoints:
 
Treatment-emergent adverse events (TEAEs).Clinical safety laboratory test results.Vital sign measurements including orthostatic blood pressure and pulse rate.Body weight.Electrocardiography (ECG) findings.Physical examination findings.Suicidal ideation and behavior as measured by the Columbia Suicide Severity Rating Scale (C-SSRS) score.Dissociative symptomatology as measured by Clinician Administered Dissociative State Scale (CADSS) score.Psychopathology severity as measured by Brief Psychiatric Rating Scale Positive Subscale (BPRS+) score.

Objectives	Endpoints
	• [REDACTED]
Exploratory Objective: To characterize the effect of SPN-820 on brain-derived neurotrophic factor (BDNF) concentrations.	Exploratory Endpoint: 
CFB to each time point for BDNF concentrations.

2. STUDY DESCRIPTION

2.1. Study Design

This is an open-label study of SPN-820 administered orally once every 3 days for a 7-day treatment period in adult subjects with major depressive disorder (MDD). The study consists of a 28-day screening period, a 10-day evaluation period (clinic and home), and a safety follow-up phone call approximately 5 (+2) days after the last administration of study medication (SM). The total study duration from the screening visit to completion of the safety follow-up phone call is up to 40 days.

2.2. Schedule of Visits and Study Procedures

The Schedule of Events and Assessments for the study is shown in Section [1.1](#).

2.3. Study Treatment

SM will be administered orally in the clinic once every 3 days for a 7-day treatment period. SM should be administered in the morning, approximately 3 hours after breakfast.

Subjects will receive a single dose of SPN-820 2400 mg as six 400 mg capsules on days 1, 4, and 7.

Subjects who cannot tolerate SPN-820 2400 mg should be discontinued from the study at the discretion of the Investigator.

Subject will not receive SM on days 2, 3, 5, 6, 8, 9, or 10.

2.4. Randomization

Not applicable.

2.5. Blinding

Not applicable.

2.6. Sample Size

Approximately 50 subjects will be enrolled to achieve about 40 subjects completing the study. This sample size is based on clinical judgement without a formal, statistical power calculation.

3. GENERAL CONSIDERATIONS FOR DATA ANALYSES AND HANDLING

3.1. General Statistical Methods

All statistical analysis will be performed using SAS version 9.4 or higher. All data will be summarized for the SPN-820 treatment group.

Continuous variables will be summarized descriptively using number of subjects (n), mean, standard deviation (SD), median, first quartile (Q1), third quartile (Q3), minimum, and maximum.

Categorical variables will be summarized descriptively using counts and percentages. When the denominator for the percentage is different from the number of subjects in the treatment column header of a summary table, the denominator will be specified in a footnote for the table.

Individual subject data will be listed by subject ID. Unscheduled measurements (unless defined as baseline or otherwise specified) will be excluded from summary tables but will be included in data listings. For assessments that are repeated or unscheduled for a visit, unless otherwise specified, the non-missing values from the first assessment will be used for generating summary statistics.

3.2. Definitions and Derivations

The definitions and derivations are shown in Table 2.

Table 2: Definitions and Derivations

Terminology	Definition
Baseline	Unless specified otherwise, baseline is the last non-missing assessment collected before the first dose of SM (Day 1).
Study Day	Day 1 is defined as the date of the first dose of study medication. For visits prior to Day 1, Study Day is calculated as (Event date – Day 1). For visits after Day 1, Study Day is calculated as (Event date – Day 1 + 1).
Screened Subjects	Subjects who have provided signed informed consent.

3.3. Analysis Population

The full analysis set (FAS) includes all subjects who receive at least one dose of SM, and have a baseline and at least one post-baseline measurement of HAM-D₆.

The Safety Population includes all subjects who receive at least one dose of SM.

The Pharmacodynamics (PD) Population includes all subjects who receive at least one dose of SM and have a baseline and at least one valid post-baseline BDNF concentration.

3.4. Data Pooling

Data from all sites will be pooled together for all analyses unless otherwise specified.

3.5. Adjustments for Covariates

Not Applicable.

3.6. Hypotheses

Not Applicable.

3.7. Multiplicity Adjustments

Not Applicable.

3.8. Subgroups

No subgroup analyses are planned.

3.9. Handling of Missing Data

3.9.1. Missing Efficacy Endpoints

Missing efficacy endpoints will not be imputed. Efficacy endpoints will be summarized on an observed-case basis.

3.9.2. Missing Dates for Adverse Events and Concomitant Medication

Missing dates for adverse events (AEs) and concomitant medications will be imputed according to the rules in Table 3.

Table 3: Missing Date Imputation for Adverse Event or Concomitant Medication

Missing Date Pattern	Imputation Rule
Partial Start Date	
Missing day only: Impute the first dose date if (1) the year and the month of the event start date are identical to those of the first dose date and (2) the event end date is not prior to the first dose date; otherwise, impute the first day of the month.Missing month only: Impute the first dose month if (1) the year of the event start date is identical to the year of the first dose date and (2) the event end date is not prior to the first dose date; otherwise, impute January.Missing month and day: Impute the first dose date if (1) the year of the event start date is identical to the year of the first dose

Missing Date Pattern	Imputation Rule
	date and (2) the event end date is not prior to the first dose date; otherwise, impute 1 st January.
Partial End Date	
• Missing day only: Impute the last day of the month or the last study date, whichever is earlier.• Missing month only: Impute December or the month of the last study date, whichever is earlier.• Missing month and day: Impute 31st December or the last study date, whichever is earlier.
Missing Year or Completely Missing Date	No Imputation will be done.

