- The follow-up assessments will be performed through a safety follow-up phone call. The safety follow-up phone call will occur approximately 5 days after the last administration of SM.
- AEs reported during screening will be recorded as part of the subject's medical history.
- A complete physical examination will be performed at screening and baseline visits; a brief physical examination will be performed at EOS/ET.
- Vital signs measurements include orthostatic blood pressure/pulse rate, respiratory rate, and oral temperature. Orthostatic blood pressure and pulse rate should be measured after the subject has been sitting for 5 minutes and again within 3 minutes of subject standing.
- ECGs should be performed prior to blood draws.
- Serology tests include human immunodeficiency 1/2 antigen/antibody, hepatitis B surface antigen, and hepatitis C virus antibody.
- A standard urine drug screen will be performed at screening and point-of-care urine drug screen together with the breathalyzer will be performed at baseline (Day 1) and all post-baseline clinic visits (days 4, 7, and 10).
- On days 2, 3, 5, 6, 8, and 9, the HAM-D₆ questionnaire will be administered remotely by telephone.
- SAEs will be captured from the time of ICF signing, and AEs will be captured following the first administration of SM and continue through the FPC.
- Seven total blood samples will be collected for measurement of BDNF concentrations: 3 pre-dose collections on days 1, 4 and 7; 3 post-dose collections 4 hours after SM administration on days 1, 4, and 7; and 1 collection on Day 10.
- Subjects will take their SM in the clinic.
- Subjects will receive a paper ADT adherence diary at screening and document the day of each dose of their ADT throughout the study. Subjects will bring their ADT adherence

diaries to each clinic visit for review of subject compliance.

m. ADT will not be provided by the Sponsor. Subject's ADT will have started and have been stable for at least 6 weeks prior to screening and will continue through the safety follow-up phone call.

Table 2: Detailed Schedule of Timed Assessments (Window)

Study Day	Clinic Visit Number	Location	Time ^a		HAM-D ₆ ^b	MADRS ^b	CGI-S	BDNF ^c
1	2	Clinic	Pre-dose		X (-60 min)	X (-60 min)	X (-60 min)	X (-60 min)
			1 hour					
			2 hours		X (±30 min)			
			4 hours		X (±30 min)	X (±30 min)		X (±30 min)
			8 hours		X (±30 min)			
2	–	Home	24 hours		X (±2 h) ^e			
3	–	Home	48 hours		X (±2 h) ^f			

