7.2.5 Recording and Evaluation of Adverse Events

All subjects who are screened will be questioned regarding any current and prior medical health status or diagnoses and any medical records will be documented as medical history. At each contact with the subject following the first administration SM on Day 1, The investigator must seek information on AEs by specific questioning and, as appropriate, by examination.

Information on all AEs should be recorded immediately in the source document, and also in the appropriate AE module of the eCRF. All clearly related signs, symptoms, and abnormal diagnostic procedure results should be recorded in the source document, though they may be grouped under one diagnosis. For example, fever, elevated white blood cell count, cough, abnormal chest X-ray, etc., can all be reported as “pneumonia.”

All AEs occurring after administration of SM throughout the study must be recorded. A TEAE is defined as an AE with a start date on or after the first dose of SM administration, or that worsened following first administration of SM. All AEs in this study will be recorded after administration of SM, therefore all will be considered TEAEs. The clinical course of each AE should be followed for at least 30 days following the date of last administration of SM (either due to EOS or ET) or until resolution, or until, in the medical judgment of the investigator, the event has stabilized or is assessed as chronic.

The investigator is responsible for evaluating AEs and determining the following:

- Serious versus non-serious: Is the event a serious adverse event (SAE)?
- Causality: Was the AE related or not related to the SM?
- Severity: How pronounced is the incapacity/discomfort caused by an AE?

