8.1. Adverse Events

All adverse events (AEs) will be coded using the MedDRA v26.1. The MedDRA version used for reporting will be specified in the footnote of the applicable output.

A treatment-emergent adverse event (TEAE) is defined as an AE with a start date on or after the date of the first dose of study medication, or that worsened in severity following the first dose of study medication. Any event that is present at baseline but worsens in severity will be determined by the Investigator and entered in the CRF as new AE. Thus, all eCRF-collected AEs that occurred on or after the date of the first dose of study medication are TEAEs.

Based on the Investigator's determination, the severity of TEAEs will be classified as mild, moderate or severe. For summaries by severity, a subject experiencing multiple AEs in the same preferred term with different intensities will only be counted once with the maximum severity. If severity is missing, then the maximum severity will be assumed for the analysis (i.e., severity = severe).

The relationship between the study medication and a TEAE is determined by the Investigator and will be classified as unrelated (i.e., unlikely related and not related) or related (possibly related and definitely related). TEAEs with missing relatedness will be counted as definitely related. For summaries by relationship, a subject experiencing multiple AEs in the same preferred term with different relationship will only be counted once with the most related occurrence.

An overview of TEAE will include summaries of number and percent of subjects who had at least one TEAE, Treatment-emergent serious AE (SAE), Treatment-emergent SAEs related to SM, TEAE leading to death, TEAE by maximum severity, TEAE by relationship, and TEAE leading to withdrawal of study medication.

In addition to the overview of TEAE summary, the following TEAEs summary tables will be provided:

- Treatment-Emergent Adverse Events by System Organ Class and Preferred Term
- Most Common ($\geq 5\%$) Treatment-Emergent Adverse Events by Preferred Term
- Treatment-Emergent Adverse Events by System Organ Class, Preferred Term, and Severity
- Treatment-Emergent Adverse Events by System Organ Class, Preferred Term, and Relationship to Study Medication
- Treatment-Emergent Serious Adverse Events by System Organ Class and Preferred Term
- Treatment-Emergent Adverse Events Leading to Withdrawal of Study Medication by System Organ Class and Preferred Term

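### When only the month of an AE start is missing, the SAP's imputation rule can date a post-dose event before the first dose, so the event can miss the TEAE tables

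*SAP*

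**What the plan says.** SAP 3.9.2, Table 3, has three rules for partial start dates. Each applies its main branch only if the event's end date is not before the first dose.

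- Day missing: "Missing day only: Impute the first dose date if (1) the year and the month of the event start date are identical" (the comparison is with the month and year of dosing). Otherwise the first of the recorded month is used.
- Month missing: "Missing month only: Impute the first dose month if (1) the year of the event start date is identical to the year" (that is, the dosing year). Otherwise January is used. The recorded day stays.
- Month and day missing: "Missing month and day: Impute the first dose date if (1) the year of the event start date is identical to the year" (again, the dosing year). Otherwise 1 January is used.

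For a missing year or a wholly missing date, the entry is "No Imputation will be done".

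SAP 8.1 says that a TEAE "is defined as an AE with a start date on or after the date of the first dose of study medication", or an event that worsened in severity after that dose. It adds: "Thus, all eCRF-collected AEs that occurred on or after the date of the first dose of study medication are TEAEs". The AE summary tables listed there are TEAE tables. Missing severity is counted as severe and missing relatedness as definitely related, but no default is given for a start date that cannot be placed.

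Protocol 7.2.5 gives the same start-date definition in substance and then says: "All AEs in this study will be recorded after administration of SM, therefore all will be considered TEAEs". On capture, Protocol Section 6 (Table 1 footnotes) says: "SAEs will be captured from the time of ICF signing, and AEs will be captured following the first administration of SM". SAP Section 9 declares no change from the protocol's planned analyses.

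**The concern.** The day-missing and month-and-day-missing rows can fall back on the first-dose date itself. The month-missing row falls back only on the first-dose month and joins it to whatever day was recorded. If dosing was late in a month and the event began early in the next, the result is a date weeks before dosing.

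The end-date condition suggests that the table means to keep any event that could have begun after dosing. This row does not achieve that. A programmer who applies Table 3 and then the date test in SAP 8.1 would flag such an event as not treatment-emergent.

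Safety and tolerability is a secondary objective. With about 50 subjects, one subject more or less is visible in an incidence table.

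**Working it through.** The plan states no figure for this point, so there is none to reproduce. The check applies the Table 3 rules to every possible case.

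**Inputs**
- Imputation rules: SAP 3.9.2, Table 3.
- AE capture: from the first dose to the follow-up call, which falls 5 (+2) days after the Day 7 dose, so Day 12 to Day 14 (Protocol 4.1 and Table 1).
- Sample size: about 50 enrolled, about 40 completing (Protocol 8.2).
- Assumptions, not from the documents: first-dose dates uniform over a 366-day year, onset uniform over Days 1 to N, and end date not before the first dose.

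**One case**
- First dose 28 March; AE start recorded as day 03, month unknown, same year; end 05 April.
- The year matches and the end date is not before dosing, so the rule gives 03 March.
- That is 28 − 3 = 25 days before the first dose. The start consistent with post-dose collection is 03 April (Day 7).

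**All cases, month missing**
- Failure occurs when onset falls in the calendar month after dosing, within the same year. Onset is then at most 13 days after dosing, so the recorded day is always smaller than the first-dose day and the imputed date is always before dosing.
- Each month boundary contributes 1 + 2 + … + (N − 1) = N(N − 1)/2 failing pairs of first-dose date and onset day.
- Eleven boundaries count. The December-to-January boundary does not, because the year differs and the rule then imputes January, which is correct.
- Share misplaced = 11 × N(N − 1)/2 ÷ (366 × N).

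| Onset window | Misplaced pairs | All pairs | Share |
|---|---|---|---|
| Days 1–10 | 11 × 45 = 495 | 3,660 | 13.5% |
| Days 1–12 | 11 × 66 = 726 | 4,392 | 16.5% |
| Days 1–14 | 11 × 91 = 1,001 | 5,124 | 19.5% |

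Direct enumeration of every pair gives the same counts.

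**The other two partial-date rows**
The same enumeration gives 0% misplaced for each. The start becomes the first-dose date, or the first day of a later month or year.

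**What one subject is worth**
- 1/50 = 2.0 percentage points; 1/40 = 2.5.
- If one of three subjects with a preferred term were lost, the term would go from 3/50 = 6% to 2/50 = 4%, below the 5% cut for the common-TEAE table. This illustrates sensitivity and does not predict a loss.

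**The case against.** The strongest reply is that the documents never say these events are excluded. Protocol 7.2.5 makes every recorded AE a TEAE, non-serious AEs are collected only after dosing, and SAP Section 9 declares no departure from the protocol. A programmer could keep the event on those grounds. The pattern is also odd: contact is scheduled on each of Days 1 to 10 and again by telephone at about Day 12, and Protocol 9.3.3 provides for data queries, so a known day beside an unknown month should usually be resolved. All AEs are listed, and this single-group study tests no hypothesis.

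Most of this stands. It limits the size of the problem and makes exclusion a possibility, not a certainty. It does not rescue the rule, which produces a wrong date on its own terms. SAP 8.1 also keeps a date condition in its sentence on eCRF-collected events, so the two readings lead to different tables.

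A reader might infer three stronger things that the documents do not support.

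- That such events drop out of every TEAE table. This needs the date test to override the protocol's all-AEs sentence, and neither document says that it does.
- That the SAP contradicts the protocol's TEAE definition. The protocol has the same definition, including the limb for worsening events. The tension lies between two sentences within Protocol 7.2.5 and is carried into the SAP.
- That the error runs only towards losing events. SAEs are captured from consent. A screening SAE that began on 20 February and is ongoing, with the month missing and a first dose on 10 March, would be dated 20 March and become treatment-emergent.

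**Conclusion.** The month-missing row of SAP Table 3 is defective. It can place a true post-dose onset before dosing, and the event can then fail the SAP 8.1 test and be left out of the TEAE summaries.

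The share affected is 16.5% of month-missing AEs for onset on Days 1 to 12, and 19.5% for Days 1 to 14. Both figures rest on uniform first-dose dates and uniform onset, and they apply only to AEs with day and year recorded and month absent. The documents do not say how often that occurs; it is likely rare. The other two partial-date rows are not affected.

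It might also be inferred that every AE with a missing year or a wholly missing date fails the TEAE definition. That goes too far: its status is left unstated, and the all-AEs sentence in Protocol 7.2.5 would largely settle it. It is worth one sentence for consistency.

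Overall this is a minor specification gap. No loss of events is demonstrated.

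**What to change.** **SAP 3.9.2, Table 3.** For AEs with only the month missing and an end date not before the first dose, keep the recorded day. Impute the earliest month that puts the start on or after the first dose and not after the end date or the last study date. If no such month exists, use the first-dose date.

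In the worked case this gives 03 April and keeps the recorded day; simply resetting early dates to the first-dose date would give 28 March and overwrite it. The same day number recurs no sooner than 28 days later, and onset on Days 1 to 14 is at most 13 days after dosing. The earliest admissible date is therefore the true one, and the misplaced share falls to 0%.

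**SAP 8.1.** State that an AE whose start date cannot be placed counts as a TEAE unless its end date is before the first dose or it is an SAE documented during screening.

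**Cost.** Two short additions to the SAP and a small programming change. An occasional pre-dose event may be counted as a TEAE; an ongoing screening SAE with a missing month could still be dated after dosing under the new month rule. That is the conservative direction the SAP already takes for missing severity and relatedness.
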